4.1.1 Pharmaceutical and Therapeutic Background

The importance of intact immune surveillance function in controlling outgrowth of neoplastic transformations has been known for decades (Disis, 2010). Accumulating evidence shows a correlation between tumor-infiltrating lymphocytes in cancer tissue and favorable prognosis in various malignancies. In particular, the presence of CD8+ T-cells and the ratio of CD8+ effector T-cells/FoxP3+ regulatory T-cells (T-reg) correlates with improved prognosis and long-term survival in solid malignancies, such as ovarian, colorectal, and pancreatic cancer; hepatocellular carcinoma; malignant melanoma; and renal cell carcinoma. Tumor-infiltrating lymphocytes can be expanded ex vivo and reinfused, inducing durable objective tumor responses in cancers such as melanoma (Dudley et al., 2005; Hunder et al., 2008).

The PD-1 receptor-ligand interaction is a major pathway hijacked by tumors to suppress immune control. The normal function of PD-1, expressed on the cell surface of activated T-cells under healthy conditions, is to down-modulate unwanted or excessive immune responses, including autoimmune reactions. PD-1 (encoded by the gene *Pdcd1*) is an immunoglobulin (Ig) superfamily member related to cluster of differentiation 28 (CD28) and cytotoxic T-lymphocyte-associated protein 4 (CTLA-4) that has been shown to negatively regulate antigen receptor signaling upon engagement of its ligands (PD-L1 and/or PD-L2) [Greenwald et al., 2005; Okazaki et al., 2001].

The structure of murine PD-1 has been resolved (Zhang et al., 2004). PD-1 and its family members are type I transmembrane glycoproteins containing an Ig-variable-type (IgV-type) domain responsible for ligand binding and a cytoplasmic tail responsible for the binding of signaling molecules. The cytoplasmic tail of PD-1 contains 2 tyrosine-based signaling motifs, an immunoreceptor tyrosine-based inhibition motif, and an immunoreceptor tyrosine-based switch motif. Following T-cell stimulation, PD-1 recruits the tyrosine phosphatases, SHP-1 and SHP-2, to the immunoreceptor tyrosine-based switch motif within its cytoplasmic tail, leading to the dephosphorylation of effector molecules such as CD3 zeta (CD3 ζ), protein kinase C-theta (PKC θ), and zeta-chain-associated protein kinase (ZAP70), which are involved in the CD3 T-cell signaling cascade [Okazaki et al., 2001; Chemnitz et al., 2004; Sheppard et al., 2004; and Riley, 2009]. The mechanism by which PD-1 down-modulates T-cell responses is similar to, but distinct from, that of CTLA-4, because both molecules regulate an overlapping set of signaling proteins [Parry et al., 2005; Francisco, 2010]. As a consequence, the PD-1/PD-L1 pathway is an attractive target for therapeutic intervention in cervical cancer.

On June 12, 2018, the FDA approved pembrolizumab for patients with recurrent or metastatic cervical cancer with disease progression on or after chemotherapy whose tumors express PD-L1 (CPS ≥ 1) as determined by an FDA-approved test. The accelerated approval was based on the results of KEYNOTE 158 (NCT02628067). Pembrolizumab was investigated in 98 patients with recurrent or metastatic cervical cancer enrolled in a single cohort of a multicenter, non-randomized, open-label, multi-cohort trial. Patients were treated with pembrolizumab intravenously at a dose of 200 mg every 3 weeks until unacceptable toxicity or documented disease progression [Chung, 2019].

Among the 98 patients, 82 (83.7%) patients had tumors that expressed PD-L1 with a CPS ≥ 1 PD-L1 status was determined using the PD-L1 IHC 22C3 pharmDx Kit. The major efficacy outcomes were objective response rate (ORR) according to RECIST 1.1 as assessed by blinded independent central review, and response duration. With a median follow-up time of 10.2 months, the ORR was 12.2%

(95% CI: 6.5 to 20.4%), including three complete responses and nine partial responses. All 12 responses were in patients with PDL-1 positive tumors, for an overall response rate of 14.6% (95% CI, 7.8 to 24.2%). The estimated median response duration was not reached (range ≥ 3.7 to ≥ 18.6 months). Treatment related grade 3 to 4 adverse events (diarrhea, asthenia, pyrexia, arthralgias and increase in AST) occurred in 12.2% of patients.

PARP inhibition has been evaluated in several randomized controlled trials. Olaparib was evaluated in two randomized, placebo-controlled double-blind, multi-center studies in patients with recurrent ovarian cancers who were in response to platinum-based therapy. SOLO-2 evaluated patients with a gBRCAm, who had a response to platinum based therapy. These patients were then randomized to maintenance therapy with olaparib. The patient who received olaparib had a PFS 19.1 months compared to 5.5 months in the control arm [Pujade-Lauraine et al., 2017]. STUDY 19 also evaluated olaparib as maintenance therapy for recurrent ovarian cancer, regardless of BRCA status and also demonstrated a PFS advantage to those women receiving olaparib maintenance [Ledermann et al., 2012]. The POLO trial evaluated olaparib for gBRCAm metastatic pancreatic cancer [Golan et al, 2019]. Maintenance olaparib demonstrated a longer PFS for this cohort of pancreatic cancer patients.

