4.2.3 Rationale for Endpoints

4.2.3.1 Efficacy Endpoints

The primary clinical endpoint is overall Objective Response Rate by iRECIST criteria (iORR).

Secondary clinical endpoints will include Progression Free Survival (PFS) and Overall Survival (OS) and safety and tolerability per the Common Terminology Criteria for Adverse Events (CTCAEv5.0) (Common Terminology Criteria for Adverse Events https://ctep.cancer.gov/protocoldevelopment/electronic_applications/docs/CTCAE_v5_Quick_Reference_8.5x11.pdf. Accessed September 30, 2018).

Although cervical cancer is curable in early stages, once it has recurred or metastasized less than 20% of patients survive 5 years (Howlader et al., 2017). Pembrolizumab was recently approved for treatment of PD-L1 positive cervical cancer patients in the second line metastatic setting, with an ORR of only 12.2% in the general population on study (Chung et al., 2019). A proposed model to increase pembrolizumab activity is through increasing tumor mutational load and formation of neoantigens expressed on cancer cells, thereby leading to greater recognition of those tumor cells by the immune system (Rizvi et al., 2015; Snyder et al., 2014; Van Allen et al., 2015). This strategy could be achieved through either enriching treated populations with cancer patients harboring innate (germline or somatic) DNA repair deficiencies, by combining immune checkpoint inhibitors with compounds causing DNA damage, such as platinum and other alkylating agents, or using compounds that directly inhibit DNA repair, such as (PARP) inhibitors.

Olaparib is an oral inhibitor of PARP, causing synthetic lethality in BRCA1/2 deficient tumors and is FDA approved for the treatment of metastatic breast and ovarian cancers harboring germline mutations in the BRCA genes or as maintenance in ovarian cancer patients with tumors experiencing prior sensitivity to platinum agents [Pujade-Lauraine et al., 2017; Robson et al., 2017; Ledermann, et al., 2012].

We expect that the combination of pembrolizumab and olaparib in patients with advanced cervical cancer after failure of chemotherapy will lead to increased efficacy compared to single agents in this population, and that the increase in efficacy will be substantial in those patients harboring homologous recombination repair and other deficiencies in DNA damage repair. We also expect that the combination will be safe and tolerable without significant overlapping toxicities.

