6.1.2.6.5 RECIST 1.1 Assessment of Disease

RECIST 1.1 will be used as the primary measure for assessment of tumor response, date of disease progression, and as a basis for all protocol guidelines related to disease status (eg, discontinuation of study treatment). Although RECIST 1.1 references a maximum of 5 target lesions in total and 2 per organ, the Sponsor allows a maximum of 10 target lesions in total and 5 per organ, if clinically relevant to enable a broader sampling of tumor burden.

6.1.2.6.6 iRECIST Assessment of Disease

iRECIST is based on RECIST 1.1 but adapted to account for the unique tumor response seen with immunotherapeutic drugs. When clinically stable, participants should not be discontinued until progression is confirmed by the Investigator, working with local radiology, according to the rules below. This allowance to continue treatment despite initial radiologic PD takes into account the observation that some participants can have a transient tumor flare in the first few months after the start of immunotherapy, and then experience subsequent disease response.

[figure not shown]
A description of the adaptations and iRECIST process is provided in Appendix 4, with additional detail in the iRECIST publication [Seymour et al., 2017]. iRECIST will be used by the Investigator to assess tumor response and progression, and make treatment decisions.

Table 8 Imaging and Treatment after First Radiologic Evidence of Progressive Disease

	Clinically Stable		Clinically Unstable	
	Imaging	Treatment	Imaging	Treatment
First radiologic evidence of PD by RECIST 1.1	Repeat imaging at 4 to 8 weeks to confirm PD	May continue study treatment at the Investigator's discretion while awaiting confirmatory tumor imaging by site by iRECIST	Repeat imaging at 4 to 8 weeks to confirm PD per Investigator's discretion only	Discontinue treatment
Repeat tumor imaging confirms PD (iCPD) by iRECIST per Investigator assessment	No additional imaging required	Discontinue treatment (exception is possible upon consultation with Sponsor)	No additional imaging required.	Not applicable
Repeat tumor imaging shows iUPD by iRECIST per Investigator assessment	Repeat imaging at 4 to 8 weeks to confirm PD. May occur at next regularly scheduled imaging visit	Continue study treatment at the Investigator's discretion	Repeat imaging at 4 to 8 weeks to confirm PD per Investigator's discretion only	Discontinue treatment

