7.0 STATISTICAL ANALYSIS PLAN

7.1 Statistical Analysis Plan Summary

7.2 Statistical Analysis Plan

Sample size calculation: Single-Stage design will be used for this study [A'Hern, 2001; Fleming, 1982]. The study will require 48 subjects to decide whether the proportion responding (P), is less than or equal to 0.130 or greater than or equal to 0.280. If the number of responses is 10 or more, the hypothesis that $P \leq 0.130$ is rejected with a target error rate of 0.100 and an actual error rate of 0.087. If the number of responses is nine or less, the hypothesis that $P \geq 0.280$ is rejected with a target error rate of 0.100 and an actual error rate of 0.099.

Efficacy analyses: The iORR will be defined as the proportion of patients with an “immune” complete response (iCR) or “immune” partial response (iPR). For the primary iORR analysis in all the treated population, patients with an iCR or iPR will be counted as successes and all other patients (including those with missing response information) will be counted as failures. The percentage of iORR with its 95% confidence interval (CI) will be presented.

Progression free survival (PFS) will be defined among all treated patients as the time from first dose of study drug until the first date of either disease progression or death due to any cause. The date of disease progression will be defined as the earliest date of disease progression based on central review. For patients whose disease has not progressed at the time of the analysis, censoring will be performed using the date of the last valid disease assessment. The data will be analyzed by the Kaplan-Meier method. The median PFS time and 95% CI will be recorded.

Overall survival (OS): Median OS will be defined as the time from the beginning of study drug treatment until death due to any cause. For patients who have not died at the time of the analysis, censoring will be performed using the date the patient was last known to be alive. The data will be analyzed by the Kaplan-Meier method. The median OS and 95% CI will be recorded.

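### The pembrolizumab-alone benchmark counts RECIST 1.1 responses and the trial counts iRECIST responses; with no response analysis on the benchmark's criterion, the false-positive rate for a claim of improvement could exceed 10%

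*Combined protocol and SAP*

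**What the plan says.** **Benchmark.** Section 4.1.1 describes the pembrolizumab cervical cohort of 98 patients. Its major efficacy outcome was "objective response rate (ORR) according to RECIST 1.1 as assessed by blinded independent central review", with 3 complete and 9 partial responses, 12.2% (95% CI 6.5 to 20.4%). Section 4.2.3.1 uses this as the figure to improve on: "with an ORR of only 12.2% in the general population on study".

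**Primary endpoint.** Section 7.2 states for iORR that "patients with an iCR or iPR will be counted as successes and all other patients" as failures. It names no reader. Section 6.1.2.6.6 does: "iRECIST will be used by the Investigator to assess tumor response and progression, and make treatment decisions". Central review or a central vendor appears only for measurable disease at screening (6.1.2.6.1), verified progression before a second course (5.2.3) and the PFS progression date (7.2).

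**Decision rule.** Section 7.2 sets the sample size and the null: "The study will require 48 subjects to decide whether the proportion responding (P), is less than or equal to 0.130". The alternative rate is 0.280. The cut-off for success is 10 responses, and the type I error is given as 0.087 against a target of 0.100. No source is given for 0.130, and no RECIST 1.1 or centrally read analysis of response is planned.

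**How the criteria relate.** Appendix 4 says the two do not differ until RECIST 1.1 progression. After that, unconfirmed progression can resolve to iSD, iPR or iCR. Section 2.0 describes pseudo-progression as rare.

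**The concern.** Section 4.2.1 sets out to show that olaparib increases the efficacy of pembrolizumab. With no control arm, that rests on comparing the trial's response count with a historical rate, so the two should be measured in the same way. Here they differ in criterion and in reader.

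The criterion difference has a known direction. A patient who progresses by RECIST 1.1 and later meets iPR or iCR counts as a success here. In a RECIST 1.1 analysis that stops at first progression, the same patient is a non-responder. The plan gives room for this, because Table 8 allows treatment to continue after a first RECIST 1.1 progression in clinically stable patients. No patient moves the other way.

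One responder in 48 is 2.1 percentage points. If the count lands on or just above 10, readers could not tell from the planned analyses whether the criterion or the added drug carried it over the line.

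**Working it through.** **Inputs.** From section 7.2: n = 48, success at 10 or more responses, null 0.130, alternative 0.280, stated errors 0.087 and 0.099. From section 4.1.1: benchmark 12/98 = 12.24%. The number of responses added by the criterion is not in the documents, so it is an assumption and is shown as a range.

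**Formula.** For a true response rate p as measured in this trial,

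P(X ≥ 10) = Σ from x = 10 to 48 of C(48, x) · p^x · (1 − p)^(48 − x).

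**Step 1: reproduce the plan.** At p = 0.130 this is 0.0865, the stated 0.087. At p = 0.280 it is 0.9005, so the type II error is 1 − 0.9005 = 0.0995 (0.09946 unrounded), the stated 0.099. The design is computed correctly for the hypothesis it states.

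**Step 2: add responses that come from the criterion alone.** Suppose olaparib adds nothing, and scoring by iRECIST raises the pembrolizumab-alone rate by d points.

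| d (assumed) | Starting from the 13.0% null | Starting from 12/98 = 12.24% |
|---|---|---|
| 0 | 0.087 | 0.063 |
| 1 point | 0.126 | 0.095 |
| 2 points | 0.174 | 0.137 |
| 3 points | 0.230 | 0.187 |
| 1 patient in 48 (2.08 points) | 0.178 | 0.141 |

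**Step 3: find where the 10% target is passed.** P(X ≥ 10) = 0.10 at p = 13.37%.

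- Above the null: 13.37 − 13.00 = 0.37 points, or 0.0037 × 48 ≈ 0.18 of a patient.
- Above the benchmark: 13.37 − 12.24 ≈ 1.12 points before rounding, or 0.0112 × 48 ≈ 0.54 of a patient.

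The rule therefore has little headroom, but it has some. A shift of less than about 1.1 points on the benchmark leaves the error at or below 10%.

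**The case against.** Several parts of the case on the other side stand.

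- **The size is unknown.** A reader might infer that the false-positive rate is above 10%. The documents do not support that. They give no rate of response after progression and call pseudo-progression rare, and a 1-point shift on 12/98 leaves the error at 9.5%.
- **The reader effect has no stated direction.** It is tempting to say that unblinded investigators over-read relative to a blinded panel. Nothing in the documents says so, and it is not claimed here.
- **The source of 0.130 is inferred.** A reader might treat the gap between 12.2% and 13% as a deliberate 0.8-point allowance for measurement. Section 7.2 does not say so, and the stated 0.087 is exact for P ≤ 0.130. The doubt concerns carrying that error rate over to a claim against pembrolizumab alone.
- **The criterion is not fully settled.** Section 6.1.2.6.5 makes RECIST 1.1 the main measure of tumor response, while sections 3.1, 4.2.3.1 and 7.2 define the primary endpoint by iRECIST. If RECIST 1.1 governed, the criterion difference would vanish and the reader difference would remain.
- **The benchmark is itself imprecise.** Its interval of 6.5 to 20.4% is wider than any shift considered here. That is a general limit of a single-arm design. It does not justify leaving an avoidable difference of known direction in place.

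**Conclusion.** The mismatch in criterion is in the documents, it can only add responders, and nothing in section 7.2 lets a reader see its effect. It could raise the false-positive rate for a claim of improvement over pembrolizumab alone: to 12.6% if the no-benefit rate as measured is 14%, and to 17.4% if it is 15%. Both rates are assumed examples. With no added responses the error stays at the stated 8.7%, or 6.3% if the true rate is 12/98.

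This rests on three things: section 7.2's definition of iORR as the governing one, the inference that 12.2% lies behind the 13% null, and an added-response rate that the documents do not give. The point supports adding an analysis. It does not show that the design is wrongly computed or that the error target is in fact missed.

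**What to change.** In section 7.2:

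1. Keep iORR with the rule of at least 10 in 48 as the primary analysis.
2. Add a prespecified supportive response rate by RECIST 1.1: best response up to first RECIST 1.1 progression, from the same reads, with its exact confidence interval and its count shown against the same 10-of-48 threshold.
3. List separately the responders who count only because of iRECIST.
4. Base any comparison with 12.2% on the RECIST 1.1 figure, and state that the benchmark was centrally read, so the reader difference remains.

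The primary conclusion should not be made formally conditional on the second count. That would cost power: if the RECIST 1.1 rate were 27%, 26% or 25% when iORR is 28%, the chance of reaching 10 would fall from 90% to about 87%, 84% or 80%.

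The cost is SAP wording and one derived variable. By Appendix 4 the RECIST 1.1 assessment already exists up to first progression, so no new scans or readers are needed. The downside is that the comparison with pembrolizumab alone may look slightly less favourable.

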4.1.2 Preclinical and Clinical Trial Data

Refer to the Investigator's Brochure for Preclinical and Clinical data.

4.1.3 The Interplay between DNA repair deficiency and Immune Checkpoint inhibition

Le et al. reported a Phase II study evaluating the clinical activity of pembrolizumab, in 41 patients with progressive metastatic carcinoma with or without mismatch-repair deficiency [Le et al., 2015]. The immune-related objective response rate and immune-related progression-free survival rate were 40% (4 of 10 patients) and 78% (7 of 9 patients), respectively, for mismatch repair-deficient colorectal cancers and 0% (0 of 18 patients) and 11% (2 of 18 patients) for mismatch repair-proficient colorectal cancers. The median progression-free survival and overall survival were not reached in the cohort with mismatch repair-deficient colorectal cancer but were 2.2 and 5.0 months, respectively, in the cohort with mismatch repair-proficient colorectal cancer.

Interestingly, patients with mismatch repair-deficient non-colorectal cancer had responses similar to those of patients with mismatch repair-deficient colorectal cancer (immune-related objective response rate, 71% [5 of 7 patients]; immune-related progression-free survival rate, 67% [4 of 6 patients]). Whole-exome sequencing revealed a mean of 1782 somatic mutations per tumor in mismatch repair-deficient tumors, as compared with 73 in mismatch repair-proficient tumors ($P=0.007$), and high somatic mutation loads were associated with prolonged progression-free survival ($P=0.02$). Since somatic mutations have the potential to encode "non-self" immunogenic antigens the authors hypothesized that tumors with a large number of somatic mutations due to mismatch-repair defects may be susceptible to immune checkpoint blockade.

Vergote et al. is evaluating the combination of pembrolizumab to traditional carboplatin and paclitaxel followed by olaparib maintainence therapy, KEYLYNK-001, as first line treatment in BRCA-nonmutated patients with advanced epithelial ovarian cancer [Vergote et al., 2019]. Similarly, KEYLYNK-009 is evaluating efficacy of olaparib plus pembrolizumab with chemotherapy plus

pembrolizumab after induction with first-line chemotherapy plus pembrolizumab in triple negative breast cancer (TNBC). The primary hypotheses are that olaparib plus pembrolizumab prolongs progression-free survival (PFS) compared with chemotherapy plus pembrolizumab.

4.2 Rationale

4.2.1 Rationale for the Trial and Selected Population

The overarching hypothesis for this trial is that the combination of pembrolizumab and olaparib in patients with advanced cervical cancer will increase the efficacy of pembrolizumab in this population, and that the increase in efficacy will be more marked in those patients harboring recombination repair deficiencies in their tumors. We also hypothesize that the combination will be safe and tolerable without overlapping toxicities. The mechanism for enhanced response to immunotherapy would be primarily through persistence of DNA damage, leading to a greater mutational load and consequently greater neoantigen presentation, recognition by the immune system and improved effector T-cell function leading to tumor cell death. The FATS1 assay will identify those patients in which an innate (both somatic or germline) FA pathway repair deficiency exists.

Forty-eight evaluable patients will be enrolled into this study. Patients must have histologically confirmed cervical cancer that is metastatic, unresectable or recurrent and exhibit ECOG performance status (PS) of less than or equal to 2. Patients will be eligible after failure of standard of care first line therapy. Prior therapy with an immune checkpoint inhibitor (PD-1, PDL-1 or PDL-2) is not allowed. PD-L1 positivity is not required for enrollment or treatment, but all patients will have PDL-1 expression assessed by the FDA approved PD-L1 IHC 22C3 pharmDx Kit (Agilent technologies, Carpinteria, CA; standard at our institution). No prior therapy with a PARP inhibitor is allowed.

